### **Study Sample**

This study will consist of two groups of male and female patients aged 6 months-65 years with a confirmed diagnosis of a neuromuscular disease. Group 1 will consist of children with earlier-onset disease, aged 6 months through 11 years of age upon inclusion. Group 2 will consist of patients aged 12 through 65 years, which will include both patients with later-stage, early onset disease, and those with late-onset, milder disease. The inherited neuromuscular disease classifications include: muscular dystrophies, motor neuron diseases, neuromuscular junction diseases, peripheral nerve diseases, metabolic myopathies, or other congenital myopathies that fall into the NIH classification of a rare/orphan disease. In addition, patients will demonstrate evidence of at least one of the following signs of respiratory insufficiency: (1) decreased FVC <80% of age and gender-predicted, (2) decreased maximal inspiratory pressure <80% of age and gender-predicted, (3) decreased maximal expiratory pressure <80% of age and gender-predicted, (4) any routine use of supplemental oxygen or mechanically-assisted ventilation, or (5) patient report of functionally-limiting dyspnea.

We plan to enroll up to thirty subjects and analyze the data according to baseline disease severity (age-predicted pulmonary function). No power calculation is feasible for this pilot trial; however, similar studies have found significant training differences in strength with 20-30 patient cohorts. Patients will be ineligible to participate if they have required acute antibiotic therapy for an acute respiratory infection within 15 days prior to baseline screening, were prescribed systemic corticosteroids or neuromuscular blocking agents within 15 days of the baseline screening, show laboratory evidence of hepatic or hematologic failure, are currently participating in other research studies involving investigational drugs, have a diagnosis of a primary

pulmonary disease, use tobacco products, or have any other concurrent medical condition which, in the opinion of the investigators, would make the subject inappropriate to participate in the respiratory exercises.

Subjects will be recruited from other research studies conducted by the PI and Sub-Is, the neuromuscular clinic run by the study team, or by self-referral. The study will be listed on ClinicalTrials.gov and the research team's website.

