### **Design**

Patients will be considered eligible for IMST if they have been diagnosed with an inherited neuromuscular disease and show clinical evidence of impaired pulmonary function. Subjects will undergo RMST for up to 12 weeks. Pulmonary function and strength testing and a symptom questionnaire will be administered before and after IMST.

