### **Study Procedures**

Complete respiratory testing will occur before and after IMST. In conjunction with respiratory testing, baseline and exertional blood pressure, heart and respiratory rate, end-tidal CO2 and pulse oximetry will be monitored. The following tests will be completed on all subjects.

**Pulmonary Function Tests:** Subjects will complete tidal flow-volume assessments and forced expiratory maneuvers according to American Thoracic Society guidelines. Three to five trials will be administered, separated by at least 2 minutes of rest.

**Repeated Inspiratory Load Compensation:** Subjects will undergo 4 sets of 10 maximal-effort breaths against standardized resistances (one set each at 0, 5, 10, and 15 cm H2O). If a patient cannot generate at least 20% of resting tidal volume with one of the lower standardized resistances, we will forego testing with any higher loads. Trials will be separated by at least three minutes of rest.

**Maximal Respiratory Pressures:** Subjects will perform maximal inspiratory and expiratory pressure maneuvers, in accordance with American Thoracic Society testing guidelines. Trials will be administered until 5% variability is achieved between three trials (typically achieved within 5 trials), and separated by at least 2 minutes of rest.

Every attempt will be made to assist participants and their families to travel to University of Florida for respiratory testing. If the study team determines that it is not in the best interest of the eligible participant to travel for a test session, the study team will consider the option of conducting the requisite tests at a site local to the subject.

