### **Training**

**IMST Training:** All subjects will receive IMST for up to 3 months, using a commercially-available respiratory training device (depending upon initial strength: Threshold PEP or IMT devices, Philips-Respironics). Patients and their families will be instructed in the use of the assigned training device. Subjects will complete loaded breaths, at an intensity of up to 50% of maximal pressure. In the unlikely event that the subject cannot initially exercise at this intensity, the subject will exercise at the highest load that is well-tolerated (determined by full opening of the training valve, absence of dyspnea or fatigue, and stable vital signs).

The subject will be instructed to take 8-15 deep, forceful breaths through the Threshold device, followed by at least 3 minutes of rest. The process will be repeated 3 more times for a total of 4 sets of 8-15 breaths. IMST will be completed three to five days per week, based upon the subject's daily baseline level of fatigue.

Subjects and their families will be directly monitored by telephone during every IMST session for the first two weeks and receive real-time feedback to ensure proper technique and provide instruction on progression of the training. IMST will routinely occur at home, yet an investigator will continue to participate in IMST at least once per week remotely by telephone or video.

conference. We have experience in remote monitoring of IMST in ventilator-dependent children, and remotely-supervised sessions enable investigators to monitor compliance, progress the IMST load, and provide feedback.

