### **Statistical Methods**

The primary endpoints for inspiratory muscle training efficacy will include respiratory muscle strength. Secondary outcome measures include be respiratory function and breathing pattern during loaded breathing.

Changes in strength and respiratory function will be analyzed by repeated measures ANOVA.

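### The infection exclusion depends on antibiotic treatment, so recovery from an untreated or viral infection could be counted as training gain

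*Combined protocol and SAP*

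**What the plan says.** In the Study Sample section of the combined protocol and SAP, the infection exclusion applies to patients if "they have required acute antibiotic therapy for an acute respiratory infection within 15 days prior to baseline screening". A second rule with a 15-day window excludes those who "were prescribed systemic corticosteroids or neuromuscular blocking agents within 15 days of the baseline screening". Both are triggered by a treatment and counted to screening. A catch-all covers any other concurrent condition "which, in the opinion of the investigators, would make the subject inappropriate to participate in the respiratory exercises".

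One of five alternative ways to qualify is "decreased maximal inspiratory pressure <80% of age and gender-predicted"; MEP and FVC below the same threshold are two others.

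The Training section states: "All subjects will receive IMST for up to 3 months". Study Procedures states: "Complete respiratory testing will occur before and after IMST". The Design section gives the same before-and-after scheme, with training for up to 12 weeks. Under Statistical Methods, "The primary endpoints for inspiratory muscle training efficacy will include respiratory muscle strength", and changes are to be tested by repeated measures ANOVA. No covariate for recent infection is mentioned.

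**The concern.** In a before-after study without controls, an eligibility rule on recent infection helps to keep a transiently low value out of the baseline. This rule looks at whether antibiotics were needed, not at whether the patient was ill. A patient one week after a viral chest infection, never prescribed antibiotics, is not excluded by it. A patient with a mild infection treated 14 days before screening is.

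If the first patient's strength or FVC is still below its usual level at the baseline test, it may rise during up to 12 weeks of training for reasons unrelated to training. With no untrained group and no second baseline, the analysis cannot separate that rise from a training effect. The error runs in one direction, and enrolling more patients does not remove it.

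Two features of the plan add to this. Because low MIP, MEP or FVC is itself a route into the study, a temporary dip can be what admits the patient. And because the plan analyses response by baseline severity, a patient tested during recovery would look more severe at entry and then show a larger gain, which affects that comparison as well as the overall mean.

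**Working it through.** The plan states no power, effect size, SD or alpha, so there is no figure of its own to reproduce. The check has two parts: whether the text leaves the gap open, and how large the effect could be under stated assumptions.

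**1. Does anything else in the text close the gap?**

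- *Catch-all exclusion.* It asks whether a concurrent condition makes the exercises unsuitable. It sets no time window and does not ask whether the baseline is stable. A recovered patient who is fit to exercise can pass it.
- *Corticosteroid and neuromuscular-blocker rule.* It catches an infection only if one of those drugs was prescribed.
- *Repeatability of maximal pressures (Study Procedures).* The 5% criterion compares trials within one session. A patient who is uniformly below usual strength that day can meet it.
- *Design.* All subjects are trained. No control group, run-in or repeat baseline is described.
- *Analysis.* No infection term is given.

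The gap is therefore open in the text.

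**2. Inflation of the mean percent gain**

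From the documents: n = 30, the maximum enrolment. Assumed: k patients tested while recovering, each a fraction d below the usual value, full recovery by the second test, and no training effect.

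An affected patient starts at (1 - d) of usual and ends at usual, an apparent gain of 1/(1 - d) - 1. Averaged over the sample:

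inflation = (k/30) × (1/(1 - d) - 1)

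| k of 30 | d = 10% | d = 20% | d = 30% |
|---|---|---|---|
| 1 | 0.37 | 0.83 | 1.43 |
| 3 | 1.11 | 2.50 | 4.29 |
| 6 | 2.22 | 5.00 | 8.57 |

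(percentage points of baseline). For example, (3/30) × (1/0.80 - 1) = 0.10 × 0.25 = 2.5 points. Partial recovery would give less.

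**3. Effect on the test**

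For one group and two time points, repeated measures ANOVA is equivalent to a paired t-test on the change. That test was simulated 40,000 times per case with no training effect. Assumed: two-sided alpha 0.05, a share f of patients recovering, and a spontaneous rise of r SDs of change in each. The spurious mean change is f × r.

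| f | r | Spurious mean change (SD) | Rejection rate, n = 30 | Rejection rate, n = 20 |
|---|---|---|---|---|
| 5% | 1.0 | 0.05 | 5.5% | 5.4% |
| 10% | 1.0 | 0.10 | 7.7% | 6.9% |
| 20% | 1.0 | 0.20 | 16.5% | 11.7% |
| 30% | 1.5 | 0.45 | 49.9% | 33.7% |

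For scale, the smallest mean change reaching significance is 0.37 SD at n = 30 and 0.47 SD at n = 20. At 5% affected, the false-positive rate hardly moves from its nominal 5%. It becomes material at roughly 20% affected or more with a large rebound.

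**The case against.** The strongest reply is that the text permits such entry but does not show that it happens. A reader might infer that recovering patients do enter and that each starts low. The documents support neither: they give no infection frequency, no depth of depression and no recovery time. Nor do they state the purpose of the exclusion, which may be safety and not baseline stability. This objection stands.

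Safeguards also exist. Investigators may use the catch-all for a patient who was ill a week ago. Vital signs, end-tidal CO2 and oximetry are monitored at testing, and section 7 refers to strict limits on them. These make entry of a visibly unwell patient less likely. They are judgements about fitness and safety, however, and do not test whether strength is back to its usual level.

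A reader might also infer that counting to screening leaves a definite gap before the baseline test. The documents do not say whether these are separate visits, and screening may include the same FVC and pressure measurements. If it is one visit, there is no gap. This part is conditional.

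Finally, the root cause is the absence of a control or repeat baseline, and a 15-day window removes only part of the problem if recovery takes longer. Both statements are right. They are reasons to add a record of infection and a sensitivity analysis; they do not justify leaving the trigger as it is.

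**Conclusion.** The point holds in a limited form. Patients recently recovered from an untreated or viral respiratory infection can enter, and in this design any natural recovery would be counted as training gain in the primary strength endpoint and in FVC. The direction is upward.

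The size cannot be derived from the documents. The range of 0.4 to 8.6 percentage points rests wholly on the assumed number affected, depth of depression and full recovery. The upper end needs 6 of 30 patients, each 30% below usual. With few patients affected the bias is negligible, so the documents do not support a conclusion that a sizeable part of any observed gain would be artefact. The change is worth making because it is cheap and the error is one-directional.

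**What to change.** Change the exclusion in the Study Sample section so that:

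- the trigger is any acute respiratory infection, whether or not treated with antibiotics;
- the protocol's own 15-day window is kept but counted to the baseline respiratory test;
- the text says which date starts the count (for example the last day of symptoms or of antibiotic treatment, whichever is later), so that nobody still under treatment is let in by the new wording;
- affected patients are deferred and may be re-screened once the window has passed.

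Because recovery may outlast 15 days, also record at the baseline test the date of any recent respiratory infection. The symptom questionnaire already given before training is a convenient place. Add to Statistical Methods a sensitivity analysis that repeats the strength and FVC analyses without patients who had a recent infection, using a look-back longer than 15 days that is fixed in advance.

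The cost is one revised eligibility sentence, one recorded item and one extra analysis. Some baseline visits would move by about two weeks. A few deferred patients, especially young children or families who travel for testing, may be deferred again or not return, which matters somewhat in a sample of up to 30.

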### **Study Procedures**

Complete respiratory testing will occur before and after IMST. In conjunction with respiratory testing, baseline and exertional blood pressure, heart and respiratory rate, end-tidal CO2 and pulse oximetry will be monitored. The following tests will be completed on all subjects.

**Pulmonary Function Tests:** Subjects will complete tidal flow-volume assessments and forced expiratory maneuvers according to American Thoracic Society guidelines. Three to five trials will be administered, separated by at least 2 minutes of rest.

**Repeated Inspiratory Load Compensation:** Subjects will undergo 4 sets of 10 maximal-effort breaths against standardized resistances (one set each at 0, 5, 10, and 15 cm H2O). If a patient cannot generate at least 20% of resting tidal volume with one of the lower standardized resistances, we will forego testing with any higher loads. Trials will be separated by at least three minutes of rest.

**Maximal Respiratory Pressures:** Subjects will perform maximal inspiratory and expiratory pressure maneuvers, in accordance with American Thoracic Society testing guidelines. Trials will be administered until 5% variability is achieved between three trials (typically achieved within 5 trials), and separated by at least 2 minutes of rest.

Every attempt will be made to assist participants and their families to travel to University of Florida for respiratory testing. If the study team determines that it is not in the best interest of the eligible participant to travel for a test session, the study team will consider the option of conducting the requisite tests at a site local to the subject.

### **Training**

**IMST Training:** All subjects will receive IMST for up to 3 months, using a commercially-available respiratory training device (depending upon initial strength: Threshold PEP or IMT devices, Philips-Respironics). Patients and their families will be instructed in the use of the assigned training device. Subjects will complete loaded breaths, at an intensity of up to 50% of maximal pressure. In the unlikely event that the subject cannot initially exercise at this intensity, the subject will exercise at the highest load that is well-tolerated (determined by full opening of the training valve, absence of dyspnea or fatigue, and stable vital signs).

The subject will be instructed to take 8-15 deep, forceful breaths through the Threshold device, followed by at least 3 minutes of rest. The process will be repeated 3 more times for a total of 4 sets of 8-15 breaths. IMST will be completed three to five days per week, based upon the subject's daily baseline level of fatigue.

Subjects and their families will be directly monitored by telephone during every IMST session for the first two weeks and receive real-time feedback to ensure proper technique and provide instruction on progression of the training. IMST will routinely occur at home, yet an investigator will continue to participate in IMST at least once per week remotely by telephone or video.

conference. We have experience in remote monitoring of IMST in ventilator-dependent children, and remotely-supervised sessions enable investigators to monitor compliance, progress the IMST load, and provide feedback.

### **Statistical Methods**

The primary endpoints for inspiratory muscle training efficacy will include respiratory muscle strength. Secondary outcome measures include be respiratory function and breathing pattern during loaded breathing.

Changes in strength and respiratory function will be analyzed by repeated measures ANOVA.

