Alternatively, respiratory muscle training may improve muscle function and delay ventilatory decline. It has been previously asserted that inspiratory muscle training (IMT) could overwork the respiratory muscles and induce fatigue in patients with neuromuscular compromise. However, the literature does not support this assumption. Among the NMDs, the majority of IMT research has been conducted in children and young adults with DMD who do not require assisted ventilation. Training-induced strength gains tend to occur more slowly in patients with neuromuscular diseases. IMT has shown effective for increasing muscle strength and endurance, regardless of disease severity. However, patients with the greatest baseline ventilatory function make the largest gains in forced expiratory maneuvers. Additionally, breathing loads are perceived as lighter by patients, following ventilatory muscle training. Patients with DMD make greater strength gains when training with high-pressure overloads, compared to low-modest resistive breathing, and have shown long term improvement in MIP, VC, and max ventilation for as long as two years.

Because previous research has primarily trained adolescents and young adults, additional knowledge is needed regarding the ability of the respiratory muscles to remodel in our youngest and older patients. Therefore, we plan to include two separate age cohorts to address these gaps. Our team safely incorporated IMST into the clinical care of critically-ill, mechanically ventilated infants with and without neuromuscular disease, including a neonate who sustained a cerebrovascular accident and an infant with Pompe disease and sepsis. We report that the intervention is both feasible and safe in infants (Smith, under review, Phys Ther). Additionally, our group has reliably assessed respiratory strength and function in boys with DMD ranging from 4 through 10 years of age (Mathur, Physiother Canada, 2009). A key objective of our laboratory is to identify the stage of disease where the greatest therapeutic benefit can be achieved. The literature suggests this could occur with earlier intervention when possible (McCool, 1995, Phys Ther), but older adults with a milder disease phenotype also stand to gain from training.

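### With two test visits and no rule for a missing post-test, classical repeated measures ANOVA estimates the gain in completers only; that is biased for the enrolled patients, in a direction the documents leave open for strength, if loss and gain both depend on baseline.

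*Combined protocol and SAP*

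**What the plan says.** The schedule has two test occasions: "Complete respiratory testing will occur before and after IMST" (Study Procedures). The analysis is one sentence: "Changes in strength and respiratory function will be analyzed by repeated measures ANOVA" (Statistical Methods). On the primary outcome, the same section says: "The primary endpoints for inspiratory muscle training efficacy will include respiratory muscle strength". Respiratory function and breathing pattern under load are secondary.

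The Study Sample section says: "We plan to enroll up to thirty subjects and analyze the data according to baseline disease severity". It gives no expected loss, effect size or SD: "No power calculation is feasible for this pilot trial; however, similar studies have found significant training differences in strength with 20-30 patient cohorts". The Design section describes one trained cohort with no control group. Nowhere do the documents define an analysis set, a rule for a missing post-test, or a sensitivity analysis.

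Two adjacent statements in the Background bear on whether gain depends on baseline. On strength: "IMT has shown effective for increasing muscle strength and endurance, regardless of disease severity". On forced expiratory function: "patients with the greatest baseline ventilatory function make the largest gains in forced expiratory maneuvers".

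Study Procedures also covers the case where it is "not in the best interest of the eligible participant to travel for a test session". The team will then consider testing nearer the patient's home.

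**The concern.** A paired comparison can use only patients with both tests. The cohort ranges from infants to adults of 65 and admits users of oxygen and assisted ventilation. Training lasts up to three months, so some post-tests may be lost, and the loss may be related to severity. If gain is also related to severity, the completers' mean gain is not the mean gain of the patients enrolled. With no control arm, no comparison exists in which the selection could cancel. At stake is which patients the main result describes, and whether its point estimate is shifted for everyone who started training.

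**Working it through.** The documents state no loss rate, effect size or SD, so there is no figure of theirs to reproduce. From the documents come the two occasions, the named method and up to 30 patients. Everything else below is an assumption.

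**1. What the named method does.** Data were simulated for 30 patients at two times, with 6 post-tests removed. A standard classical repeated measures ANOVA routine rejected the data as unbalanced. On the 24 completers it gave F = 41.35 on 1 and 23 df, equal to the squared paired t statistic. It is a completers-only paired test.

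**2. What bias requires.** Let d be the fraction lost. Then completers' gain - enrolled gain = d x (gain in completers - gain in those lost). If those lost would gain a fraction f of the completers' gain, the relative error is 1/[(1 - d) + d x f] - 1.

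| Lost | Analysed | f = 0 | f = 0.5 | f = 1 | f = 1.5 |
|---|---|---|---|---|---|
| 10% | 27 | +11% | +5% | 0% | -5% |
| 20% | 24 | +25% | +11% | 0% | -9% |
| 30% | 21 | +43% | +18% | 0% | -13% |

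For example, d = 0.2 and f = 0 gives 1/0.8 - 1 = 25%. Loss alone does nothing; those lost must also respond differently.

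**3. Size in SD units of the change.** Let z be the standardised baseline, r its correlation with the change, and let loss follow a logistic model in z. The completer bias is r x E[z | post-test present]. Integrating over a normal z, with the intercept set to give the stated loss, E[z | present] is:

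- 20% lost, log-odds 1 per SD: 0.173
- 20% lost, log-odds 2: 0.262
- 30% lost, log-odds 1: 0.253
- 30% lost, log-odds 2: 0.375

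So:

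- r = 0.3 to 0.5: from 0.3 x 0.173 = +0.05 to 0.5 x 0.375 = +0.19
- r = 0: zero
- r = -0.3: from -0.3 x 0.173 = -0.05 to -0.3 x 0.375 = -0.11

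**4. The alternative.** In a two-visit model with both visits as outcomes and unstructured covariance, the maximum likelihood gain is the completers' regression of post on pre, evaluated at the mean baseline of all enrolled, minus that mean. In 6,000 simulated trials of 30 per setting it was within 0.01 SD of the truth throughout. At r = 0.3 to 0.5 the standard error was 0.20-0.22 SD for completers and about 0.20-0.24 for the model. The largest increase, about 0.03 (0.22 to 0.25), came at r = 0 with 30% lost and log-odds 2. Root mean squared error fell from about 0.28 to 0.24 in the most adverse setting and was about equal (0.21) in the mildest. At r = 0 the model gains nothing and costs that precision.

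**5. Measurement error.** Take an assumed baseline mean of 50, SD 20, true gain 10, and the weakest 20% lost. Completers show 10.7 to 11.4 if true gain rises with baseline (slope 0.1 to 0.2), 10.0 if unrelated, and 9.3 if it falls (slope -0.1). With error of SD 5 in each test and gain unrelated to baseline they show 9.6, an understatement from regression to the mean. The likelihood estimate returned 10.0 in each case.

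**6. A trap in the remedy.** Suppose baseline percent-predicted function is added with one common slope while baseline is also an outcome. The covariate then absorbs the information that corrects for loss. With 30% lost, log-odds 2, r = 0.5 and baseline SD twice the change SD (completer bias 0.19), residual bias was about 0.05, 0.13 and 0.17 SD at covariate-baseline correlations of 0.5, 0.8 and 0.95. Omitting the covariate, or adding its visit interaction and evaluating the change at the mean of all enrolled, removed the bias.

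**The case against.** A reader might infer that the trial will overstate the strength gain because the weakest patients will drop out. The documents do not support that. The Background ties larger gains to better baseline function only for forced expiratory maneuvers. For strength it reports benefit at all severities, which does not establish equal gains but gives no direction either. The third Specific Aim plans to compare response by baseline function, so the protocol treats the question as open. Regression to the mean can push the bias downward.

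A reader might also take the travel clause as a forecast of dropout among the sickest. It is conditional, does not mention illness, and leads to an offer to consider local testing. Help with travel and at least weekly remote contact (Training) should also limit loss. These measures are real, but they neither guarantee a post-test nor say how a missing one is analysed.

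Third, repeated measures ANOVA is sometimes a loose name for a mixed model, which would keep baseline-only patients. If that is meant, one clarifying sentence is enough. The planned analysis by severity describes how gain varies, but does not bring back patients without a post-test.

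Finally, this is a pilot of up to 30, and the largest bias shown (0.19 SD) is slightly below the standard error (about 0.21 in that setting). That limits the importance of the point. It does not justify leaving the analysis set unstated.

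**Conclusion.** The concern holds in a limited form. The plan has no rule for missing post-tests, and the method it names, read classically, describes completers only. Whether that biases the gain for enrolled patients depends on two links the documents do not quantify: loss with baseline, and baseline with gain. The ranges in the working are conditional on assumed loss and correlations; they are not predictions for this trial. An upward bias has support in the documents only for forced expiratory maneuvers. For strength the sign is unknown. The case for the likelihood model does not need the sign, because it corrects baseline-related selection in either direction at small cost. It does need the loss to depend only on observed baseline. Loss driven by the unseen post-test, such as deterioration during training, would remain uncorrected. The change should be made before analysis; it is not a fatal flaw.

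**What to change.** In Statistical Methods, replace repeated measures ANOVA with a likelihood-based model for the two visits: a visit effect, unstructured covariance, both visits as outcomes, and every patient with a baseline test included. Do not add baseline percent-predicted function with a common slope. If severity is included, add its interaction with visit and evaluate the change at the mean of all enrolled patients.

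Report the completer analysis as a sensitivity analysis, state how many post-tests are missing, and compare the baseline values of completers and those lost. Add a sensitivity analysis for loss that depends on the unseen post-test, for example zero gain for those lost.

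The cost is wording in the plan, a slightly wider confidence interval, and an explicit missing-at-random assumption given baseline. No extra patients or visits are needed.
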